Study Comparing the Efficacy, Safety, and Cost of a Permanent, Synthetic Prosthetic Versus a Biologic Prosthetic in the One-stage Repair of Ventral Hernias in Clean and Contaminated Wounds.

NCT02041494

Document Date: July 23, 2014

STATISTICAL ANALYSIS PLAN

Data Analysis. The primary efficacy endpoint is the ventral hernia recurrence rate between the two treatment groups. Secondary endpoints will consist of comparisons of wound occurrences, perioperative complications, hospital length of stay, total hospital charges, pain, and quality of life. Continuous endpoints of hospital length of stay, total hospital charges, pain, and quality of life will be compared by the Mann-Whitney *U* test. The binary variables—wound infection, and perioperative complications—will be compared using Fisher's exact test. The cumulative percentages of patients with recurrences over time will be calculated and compared by using Kaplan-Meier curves and log-rank tests. We will investigate subgroup effects by comparing the size of the fascial defect (area in cm^2), patient co-morbidities, and clean versus contaminated wounds. All statistical tests will be two-sided. The primary analysis will be performed on an intention-to-treat basis for which patients will remain in their assigned group, even if during the procedure the surgeon judged the patient not to be suitable for the prosthetic or technique assigned. In addition a per-protocol analysis will also be performed for which patients with major protocol violations will be excluded.

Power Analysis: Overall, ventral hernia repairs recur with an estimated frequency of approximately 40%. However, conventional wisdom recognizes that wound contamination potentially doubles the risk of hernia recurrence. Therefore, we performed separate power analyses for hernia repairs under clean versus contaminated wound conditions that were informed by the medical literature and clinical studies we have conducted at UCSF.

Clean wounds. Published data from our medical center noted an overall hernia recurrence rate of about 20% in predominantly clean wounds [43]. Similarly, our most recent retrospective analysis indicated hernia recurrence rates of 20%-30% and 50%-60% using synthetic versus biologic mesh, respectively, regardless of wound contamination (submitted for publication). Consequently, the power analysis for ventral hernia repairs under clean conditions indicates the need for 80 patients in each group, assuming a two-sided 0.05 level test and 80% power, and hernia recurrence rates of 40% versus 20% for patients receiving biologic versus synthetic prosthetics, respectively. The estimated recurrence rate of 40% with biologic mesh is consistent with estimates from the current medical literature [32].

Contaminated wounds. If we continue to assume a two-sided 0.05 level test and 80% power, and increase the estimated hernia recurrence rate from 40% to 60% for biologic prosthetics and from 20% to 30% for synthetic prosthetics used under contaminated conditions, then we will need to enroll a total of 40 patients in each group.

In total, we plan to enroll 250 patients to account for an anticipated drop out rate of <5% (**Table 2**). It is anticipated that approximately 40-45 patients will enroll in each of the study's next two (2) years. The nine active clinicians participating the trial perform approximately 175-200 open ventral hernia repairs per year. This enrollment target should guarantee that our study is adequately powered to demonstrate a significant difference in hernia recurrence rates, if present. Importantly, we have already demonstrated the ability to randomize ventral hernia repair patients to either treatment arm, a challenge that has effectively stymied other active studies (NCT02451176).

	Assumed recurrence rate for synthetic-mesh repairs	Assumed recurrence rate for biologic-mesh repairs	Required Sample Size for both groups (N_T)
Clean wounds	20%	40%	160
Contaminated wounds	30%	60%	80

Table 2. Power analysis.

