- c) Surgical technique, to ensure a balance between hernia repairs where the prosthetic bridges the fascial defect versus reinforces a primary fascial closure*

Patients will be enrolled only once.

Patients will undergo daily evaluations during their index hospitalization. Follow-up will consist of evaluations by the investigator-surgeon before and at 1 month after surgery. The study team will perform follow-up evaluations at 3, 6, 12, 18, and 24 months after surgery or until the patient's hernia recurs. (Table 1) Due to the scheduling challenges involved, we will allow for a two-week window around the patients' targeted post-operative evaluation times. Patients will be followed for a total of 24 months since there is good evidence that the majority of hernia recurrences will take place within the first 18-24 months after surgery. [19, 20, 40, 41] Each evaluation will include a brief clinical examination, laboratory analyses, (complete cell count and differential, serum electrolytes, creatinine, urea nitrogen, albumin, prealbumin, C-reactive protein, Hgb A1c, liver function tests, urinalysis), anterior and lateral photographs of the abdomen, and ultrasound examinations of the anterior abdominal wall. During the scheduled visits wherein blood draws will occur, plasma will be banked for possible future research, considering the future potential of using antibodies as biomarkers. Evaluations of patient well-being, including a visual pain survey, Activities Assessment Score, and SF36 and HerQLes quality-of-life questionnaires (Appendices 1-4) will be performed at enrollment and 1, 6, 12 and 24 months following surgery. In addition, this panel of well-being assessments will also be administered when a patient develops a wound occurrence and/or hernia recurrence. An abdominal CT scan with intravenous contrast and volumetric analysis of the hernia will be obtained before surgery and 24 months after the hernia repair or when the patient's hernia recurs. The patient-related factors of gender, ethnicity, age, body-mass index (BMI, with obesity defined as a BMI \geq 30), chronic obstructive pulmonary disease, cough, constipation, prostatism, diabetes mellitus, glucocorticoid therapy, chronic immunosuppression, smoking status (current activity and pack-years), location of the hernia and abdominal surgery history (including prior ventral or inguinal hernia repairs) will be recorded. Perioperative factors including the patient's ASA score, size of the fascial defect (area in cm² = craniocaudal x transverse dimensions in cm), use of component separation repair techniques, duration of the operation, estimated blood loss, blood transfusion, maximum and minimum body temperature, maximum and minimum systolic blood pressure, vasopressor administration, perioperative antibiotics (including antibiotic regimen, timing of first dose and duration of therapy), postoperative complications, hospital length of stay, total hospital and professional charges and mortality will also be recorded.

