To evaluate perioperative pain we will use the visual analog scale (VAS) and quality of life using the Rand Short Form 36 (SF36), Activities Assessment Scale (AAS) and HerQLes questionnaires. The VAS and SF36 have been used to evaluate pain and quality of life outcomes in several studies of ventral hernia patients over the past several years. [7-10] Using these instruments will facilitate comparison of our results with those of other investigators. Importantly, the AAS and HerQLes quality of life tools were specifically designed and have been prospectively validated for use in patients undergoing ventral hernia repair. [11-13]

Data and Safety Monitoring Plan

Review of Safety Information. The PI, Designated Safety Officer and Internal Review Committee (IRC) will review safety data on an ongoing basis. The IRC will be composed of the PI, specialists in Infectious Diseases, Critical Care Medicine, Plastic Surgery and Biostatistics. The Designated Safety Officer will be a nurse or

research assistant with experience in clinical trial operations and safety. The IRC will prepare study data reports for review by the Data and Safety Monitoring Board.

An independent Data and Safety Monitoring Board (DSMB) will review safety data on an ongoing basis. The DSMB will be comprised of UCSF faculty and will be independent of the study team. The composition of the DSMB, as well as the schedule of activities will be made available to the NIDDK for its review. All DSMB members will review the protocol and ensure its understanding. In addition, all DSMB members will be presented with the DSMB charter and will sign a conflict of interest form.

Study Stopping Rules.

Enrollment and initiation of study treatment may be suspended at any time if any of these reviews conclude that there are significant safety concerns. If the trial is put on hold, all screening, enrollment, and initiation of any new study subjects will cease pending DSMB review.

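### Pain and quality of life are compared by a two-group rank test with no term for the enrolment score, although every instrument is measured at enrolment; this gives away precision on two secondary endpoints.

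*SAP*

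**What the plan says.** The SAP (Data Analysis) lists the secondary endpoints by domain only: "Secondary endpoints will consist of comparisons of wound occurrences, perioperative complications, hospital length of stay, total hospital charges, pain, and quality of life". For the test it says "Continuous endpoints of hospital length of stay, total hospital charges, pain, and quality of life will be compared by the Mann-Whitney" U test. It gives no baseline term, no visit, no summary over time and no lead quality-of-life instrument, and it does not state whether the score or its change from enrolment is analysed.

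The instruments are in the protocol. Under General study design they are a "visual pain survey, Activities Assessment Score, and SF36 and HerQLes quality-of-life questionnaires", and the panel "will be performed at enrollment and 1, 6, 12 and 24 months following surgery"; Table 1 shows the same schedule. The paragraph just before the Data and Safety Monitoring Plan assigns the VAS to pain and assesses "quality of life using the Rand Short Form 36 (SF36), Activities Assessment Scale (AAS) and HerQLes questionnaires". It adds that "the AAS and HerQLes quality of life tools were specifically designed and have been prospectively validated for use in patients undergoing ventral hernia repair".

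Two further statements under General study design bear on the analysis. One adds assessments triggered by events: "this panel of well-being assessments will also be administered when a patient develops a wound occurrence and/or hernia recurrence". The other limits follow-up: "The study team will perform follow-up evaluations at 3, 6, 12, 18, and 24 months after surgery or until the patient's hernia recurs".

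**The concern.** Patients are randomised in the operating room, so the enrolment score comes before treatment assignment and is a legitimate covariate. It is also normally among the best available predictors of the same instrument's later score. A two-sample rank test of follow-up scores leaves the between-patient spread that existed before surgery in the error term. The trial pays for the enrolment measurement, and the stated test has no place for it except through a change score, which the SAP does not mention.

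What is at stake is the width of the interval around each pain and quality-of-life difference, and so the chance of detecting a real one. A smaller matter goes with it. With no lead quality-of-life instrument and no lead visit for either domain, several results have equal standing, and the choice of which to present is left until after the data are in.

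**Working it through.** **The plan's own figures.** The documents give no SD, power or alpha for pain or quality of life. The sample size is for recurrence: 80 per group (clean) and 40 per group (contaminated). The unpooled two-proportion formula, n = (1.960 + 0.842)² × [p₁(1 − p₁) + p₂(1 − p₂)] / (p₁ − p₂)², reproduces it:
- clean: 7.85 × (0.24 + 0.16) / 0.04 = 78.5, so 79 against 80;
- contaminated: 7.85 × (0.24 + 0.21) / 0.09 = 39.2, so 40 against 40.

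That gives 80 + 40 = 120 per arm, used below for illustration.

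**Assumptions.** r is not in the documents and is shown at 0.3, 0.5 and 0.7. Scores are taken to have equal variance at enrolment and follow-up. A two-sided 0.05 level, which the SAP states only for recurrence, is assumed here.

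**Variance relative to raw follow-up scores.**
- Linear adjustment for the enrolment score: 1 − r².
- Change from enrolment: 2(1 − r).
- Their difference is 2(1 − r) − (1 − r²) = (1 − r)², which is never negative. Change scores therefore never beat adjustment, and they are worse than raw scores when r < 0.5.

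| Assumed r | Adjusted | Change | 120 per arm, adjusted, acts like | Detectable difference at 80% power, adjusted |
|---|---|---|---|---|
| 0.3 | 0.91 | 1.40 | 132 | 0.345 SD |
| 0.5 | 0.75 | 1.00 | 160 | 0.313 SD |
| 0.7 | 0.51 | 0.60 | 235 | 0.258 SD |

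The fourth column is 120 / (1 − r²). The unadjusted detectable difference is 2.80 × √(2/120) = 0.362 SD; the last column is 0.362 × √(1 − r²).

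**Check with the rank test itself.** The factors above are for linear models, so the Mann-Whitney test was simulated (normal scores, 120 per arm, true difference 0.362 SD, 4,000 runs):

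| Assumed r | Mann-Whitney, raw | Mann-Whitney, change | ANCOVA |
|---|---|---|---|
| 0.3 | 77% | 64% | 82% |
| 0.5 | 77% | 77% | 89% |
| 0.7 | 79% | 94% | 98% |

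The protocol plans 330 patients and the SAP 250. The variance factors do not depend on which applies; at 165 per arm the unadjusted detectable difference would be 0.308 SD.

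**Number of comparisons.** With one score per instrument, quality of life has 3 instruments × 4 postoperative visits = 12, and pain has 1 × 4 = 4. If independent and each tested at 0.05, the chance of at least one p < 0.05 under no effect is:
- quality of life: 1 − 0.95¹² = 46%;
- pain: 1 − 0.95⁴ = 19%.

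Repeated scores in the same patients are positively correlated, which lowers both figures. Subscales and event-triggered assessments would add to the counts.

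**Scores after recurrence.** The assumed recurrence rates are 40% against 20% (clean) and 60% against 30% (contaminated). If these apply by the end of follow-up, recurrences number 0.4 × 80 + 0.6 × 40 = 56 of 120 on biologic and 0.2 × 80 + 0.3 × 40 = 28 of 120 on synthetic. If scheduled assessments stop at recurrence, later scores would be missing twice as often in one arm.

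**The case against.** The strongest reply is that this is a specification gap on secondary endpoints and not an invalid analysis. Randomisation protects the unadjusted comparison, and a rank test makes few assumptions about skewed scores. That stands: leaving out the enrolment score does not bias the comparison, and neither the recurrence analysis nor its sample size is affected.

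It is also fair that the size of the gain rests on r, for which the documents give nothing. At r = 0.2 the saving is only 4% of variance, and at 0.3 it is 9%. The simulation used normal scores, so it does not settle how a model performs on skewed ones.

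A reader might infer several stronger things that the documents do not support:
- *That raw scores are planned and the enrolment scores discarded.* The SAP is silent; change scores would be consistent with its wording. They would use the enrolment score, though less efficiently than adjustment.
- *That neither domain has a named instrument.* Pain has one, the VAS; only its visit is open. For quality of life both instrument and visit are open.
- *That 16 results carry a 56% false-positive chance.* 1 − 0.95¹⁶ = 56% is correct arithmetic, but it pools two separately named endpoints and assumes independence. With between-test correlations of 0.3 to 0.8 (assumed), simulation for all 16 gave about 47% down to 21%. The per-domain figures match the SAP's endpoints.
- *That a particular visit, such as month 12, is the right one.* Nothing in the documents singles out a visit. The protocol speaks of perioperative pain for the VAS, yet collects it to month 24.

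**Conclusion.** The point holds as a loss of precision. The stated test has no term for an enrolment score that the trial collects on all four instruments, and adjusting for it would cut residual variance by 9%, 25% or 49% at assumed r of 0.3, 0.5 or 0.7. These factors are approximate and refer to linear adjustment. The ordering is firmer than the size: under equal variances, adjustment is at least as precise as raw or change scores whatever r is, apart from the negligible cost of estimating one coefficient.

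The unnamed quality-of-life instrument and the unnamed visits are a secondary gap, with at most moderate scope for selection within each domain. The handling of scores after recurrence is a separate open question and the one place where bias could enter, because recurrence is expected to differ by arm. The protocol does not say clearly that the questionnaires stop at recurrence, so this is a rule to be stated and not a demonstrated fault.

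**What to change.** In the SAP, Data Analysis:

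1. Replace the Mann-Whitney test for pain and quality of life with one model, fixed now, that adjusts for the same instrument's enrolment score: for example ANCOVA at a named visit, or a repeated-measures model over the scheduled visits. Report the adjusted difference with a 95% interval, and keep the Mann-Whitney test as a sensitivity analysis. The model should not depend on how the scores look once they are seen.
2. Before unblinded data are seen, name one lead quality-of-life instrument and one lead visit or summary for each domain. The protocol already singles out the AAS and HerQLes as hernia-specific; the visit is for the sponsor to choose and justify. Other instruments and visits become supportive.
3. State whether scheduled questionnaires continue after recurrence, how scores after recurrence enter the analysis, and whether the event-triggered assessments are used.
4. Give a simple rule for a missing enrolment score.

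Items 1, 2 and 4 change SAP wording only and add no visit or measurement, since the scores are already scheduled. Item 3 could also affect data collection if the sponsor decides that questionnaires continue after recurrence. The price is a model assumption, a missing-baseline rule, and supportive status for the remaining instruments and visits.

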Study Comparing the Efficacy, Safety, and Cost of a Permanent, Synthetic Prosthetic Versus a Biologic Prosthetic in the One-stage Repair of Ventral Hernias in Clean and Contaminated Wounds.

NCT02041494

Document Date: July 23, 2014

STUDY PROTOCOL. The specific hypothesis driving the research application is that the use of a permanent synthetic prosthetic for the one-stage repair of complex ventral hernias will result in superior outcomes compared to a biologic prosthetic.

General study design. We propose a prospective, randomized, single-blind study in 330 patients with complex ventral hernias. A permanent synthetic prosthetic will be compared to a biologic prosthetic for clinical superiority. The primary endpoint is ventral hernia recurrence rate.

Eligible patients will be randomized to undergo open ventral hernia repair using either a permanent synthetic or a biologic prosthetic. Patients will be randomized while in the operating room using a technique of stratified randomization with permuted blocks to insure a balance between the two treatment groups at study entry. Patients assigned the synthetic code will be treated using the permanent synthetic prosthetic (Ventralight®, Bard, Murray Hill, NJ), whereas those patients assigned the biologic code will be treated with the biologic prosthetic (Strattice®, LifeCell Corp., Branchburg, N.J.). The selection of the synthetic and biologic prosthetics was based on a combination of established clinical experience and our best analysis of the available preclinical data. [33-39] Ventralight is a composite product that combines a synthetic mesh with a proven absorbable hydrogel barrier to minimize tissue attachment (adhesions) to the mesh. Strattice is a non-crosslinked, terminally sterilized, porcine dermal product recently introduced in 2007. While there is limited human data available, a multi-institutional trial evaluating its outcomes during the repair of infected and contaminated hernias was recently published. [6] Prior to the random assignment to receive either a permanent synthetic or a biologic prosthetic, patients will be stratified according to 3 factors;

- a) Charlson Index score, to ensure a balance of severity in chronic illnesses of the two patient groups;*
- b) Wound contamination, to ensure a balance between clean versus contaminated repairs in the two patient groups; and*

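### Hospital length of stay is tested without the randomisation strata: the Mann-Whitney test stays valid, but it is conservative and loses power if those strata predict stay

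*SAP*

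**What the plan says.** Length of stay is a named secondary endpoint (SAP, Data Analysis): "Secondary endpoints will consist of comparisons of wound occurrences, perioperative complications, hospital length of stay, total hospital charges, pain, and quality of life". The test is given in the next sentence: "Continuous endpoints of hospital length of stay, total hospital charges, pain, and quality of life will be compared by the Mann-Whitney" *U* test. On level, the paragraph says only "All statistical tests will be two-sided".

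The Protocol (General study design) randomises "using a technique of stratified randomization with permuted blocks to insure a balance between the two treatment groups at study entry". Before assignment, "patients will be stratified according to 3 factors":

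- "Charlson Index score, to ensure a balance of severity in chronic illnesses of the two patient groups"
- "Wound contamination, to ensure a balance between clean versus contaminated repairs in the two patient groups"
- "Surgical technique, to ensure a balance between hernia repairs where the prosthetic bridges the fascial defect versus reinforces a primary fascial closure"

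The block size and the Charlson cut-points are not given. The SAP returns to co-morbidities and contamination only as subgroup comparisons, and to contamination again in sizing the recurrence endpoint. Neither use brings the strata into the length-of-stay test.

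**The concern.** Blocking within strata makes the arms nearly equal in every stratum, so differences in stay between strata can add almost nothing to the difference between arms. A two-group Mann-Whitney test does not know this. It computes its variance as if allocation had been unrestricted, so between-stratum variation stays in the denominator. If the strata predict stay, the standardised statistic is too small on average and the test rejects less often than its nominal level.

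At stake is a greater chance of missing a real difference in length of stay. Stay has no baseline measurement to adjust for, so the strata are the most direct source of precision that the design supplies.

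**Working it through.** **The plan's own figures.** The documents give no power or sample size for length of stay, so only the recurrence sizing can be reproduced. With the pooled two-proportion formula (two-sided 0.05, 80% power):

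- Clean, 40% v 20%: [1.96√(2·0.30·0.70) + 0.8416√(0.24 + 0.16)]² / 0.20² = 81.2, so 82 per group (SAP: 80).
- Contaminated, 60% v 30%: [1.96√(2·0.45·0.55) + 0.8416√(0.24 + 0.21)]² / 0.30² = 42.0, so 42 per group (SAP: 40).
- Total: 240/0.95 = 253 (SAP: 250).

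These agree closely, so N = 250 with one third contaminated (80/240, SAP Table 2) is a fair basis for the check.

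**Inputs that must be assumed.** Three binary factors giving eight strata, blocks of 4, log-normal stay in whole days with a median near 5, and a two-sided 5% level. R² is the share of log-stay variance explained by the strata. The documents do not give it, so it is varied.

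**Large-sample formulas.** With stratified allocation and an unstratified test:

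- size = 2[1 − Φ(1.96/√(1−R²))]
- power, unstratified = Φ((δ − 1.96)/√(1−R²))
- power, stratified = Φ(δ/√(1−R²) − 1.96)

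Here δ = 2.80 is the shift that gives a nominal 80%. At R² = 0.20, size = 2[1 − Φ(1.96/0.894)] = 2.8%. Power is Φ(0.84/0.894) = 83% unstratified and Φ(2.80/0.894 − 1.96) = 88% stratified.

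**Simulation at N = 250** (6,000 runs for size, 4,000 for power; shift set at nominal 80%):

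| R² | Size, Mann-Whitney | Size, van Elteren | Power, Mann-Whitney | Power, van Elteren |
|---|---|---|---|---|
| 0 | 5.0% | 5.0% | 77% | 76% |
| 0.05 | 4.4% | 5.1% | 78% | 79% |
| 0.10 | 3.8% | 4.8% | 78% | 80% |
| 0.20 | 2.8% | 4.8% | 80% | 85% |
| 0.30 | 2.2% | 5.2% | 81% | 90% |

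Under simple randomisation with R² = 0.30, the Mann-Whitney size is 4.7%. The shortfall therefore comes from pairing stratified allocation with an unstratified test.

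**Lower on the power curve.** With a shift of 0.20 on the log scale (3,000 runs), Mann-Whitney v van Elteren power is 69% v 71%, 64% v 72% and 57% v 70% at R² = 0.10, 0.20 and 0.30. Another run with that shift and a within-stratum log SD of 0.6 gives 58% v 72% at R² = 0.30. The gains are larger here because the curve is steeper.

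**More strata.** If Charlson has more levels and nothing is pooled, power for Mann-Whitney v van Elteren is:

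- 16 strata (0.20 shift): 64% v 70% at R² = 0.20, and 58% v 70% at R² = 0.30.
- 24 strata (run near 80% power): 77% v 74% at R² = 0, 78% v 78% at 0.10, and 80% v 84% at 0.20.
- 32 strata (run near 80% power): 77% v 73% at R² = 0, 78% v 77% at 0.10, and 80% v 83% at 0.20.

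**The other enrolment figure.** The Protocol states 330 patients. At N = 330 the pattern is the same: at R² = 0.20, size is 2.7% v 4.5% and power 79% v 84%. The mismatch between 330 and 250 is a separate matter.

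**The case against.** The best defence is that nothing here is an error. The Mann-Whitney test is valid, any departure is on the conservative side, and length of stay is one of several secondary endpoints with no stated effect size, power or decision rule. The 0.05 level itself appears only in the recurrence power analysis, so 5% is implied for this endpoint. All of that stands and keeps the point minor.

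The documents also offer no evidence that the strata predict stay. That stands too. At R² = 0.05 the gain is within simulation error, and with many sparse strata the stratified test can do worse. The unstratified choice is not specific to stay either: the same sentence covers charges, pain and quality of life, and the recurrence log-rank test is also described without strata.

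A reader might infer more than the documents support in three ways:

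- That a comparison with 80% power would reach about 90%. At R² = 0.25, Φ(2.80/√0.75 − 1.96) does give 90%, but the same shift gives the Mann-Whitney test Φ(0.84/√0.75) = 83% in this design, not 80%. The gain is 6 to 7 points.
- That the technique factor measures how extensive the repair is. It separates bridging from reinforcing, and the Protocol (Surgical techniques) permits component separation under both.
- That stratifying is free. It is not if the strata are uninformative or numerous.

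**Conclusion.** The point holds as an optional gain in precision. The planned test ignores the stratified allocation, and neither document uses the strata elsewhere in this comparison.

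With N = 250 and eight strata, true size is about 4%, 3% and 2% at R² of 10%, 20% and 30%. The power forgone is roughly 1-2, 5-8 and 9-14 points, depending on where on the power curve the comparison sits. This rests on assumed values for R², the number of strata, the block size and the distribution of stay. That Charlson score, contamination and technique affect stay is plausible but undocumented. If they do not, there is nothing to gain and a small amount to lose. The documents give no ground for saying that the planned comparison would be invalid or would overstate a difference.

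**What to change.** In the SAP's Data Analysis paragraph, compare hospital length of stay by a van Elteren (stratified Wilcoxon) test over the three randomisation factors. Apply the same test to hospital charges wherever a rank test is kept. Specify:

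- the factor values as entered at randomisation, since wound class and technique are also recorded at the end of the procedure and could differ;
- Charlson score grouped into a few stated levels;
- a rule for pooling small strata, fixed before unblinding;
- the unstratified Mann-Whitney test as a sensitivity analysis.

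No new data are needed, because the factors are known before assignment. The work is a short addition to the SAP, including the grouping and pooling rules, and a standard procedure. If the strata turn out not to predict stay, the cost is about 1 point of power with eight strata and about 3-4 with 32 left unpooled, which is why the grouping and pooling rules matter.

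### The secondary binary endpoints are tested by an unstratified, conservative Fisher's exact test; a stratified test with a risk difference would use the design better

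*SAP*

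**What the plan says.** The Data Analysis section of the SAP lists these outcomes as secondary: "Secondary endpoints will consist of comparisons of wound occurrences, perioperative complications" and others. "The binary variables", given there as wound infection and perioperative complications, "will be compared using Fisher's exact test". The same section adds: "All statistical tests will be two-sided". It states no stratified or adjusted version of the test, no effect measure, no confidence interval and no expected event rate for these endpoints.

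The protocol (General study design) assigns the prosthetic "using a technique of stratified randomization with permuted blocks". Beforehand, "patients will be stratified according to 3 factors": Charlson score, clean or contaminated wound, and bridging or reinforcing technique. The stated purpose is balance between the arms on each factor.

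The SAP also plans subgroup looks by defect size, co-morbidity and clean versus contaminated wounds. These explore whether the effect differs between subgroups; they do not adjust the main comparison.

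**The concern.** Two features of the planned test reduce its sensitivity. First, it pools over the strata. Stratified allocation makes the arms more alike than chance would. If a stratum predicts the outcome and the analysis ignores it, the test allows for variation that the design has already removed. Second, Fisher's test conditions on the total number of events, and the resulting discreteness keeps its true level below the nominal 5%.

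At stake is some power to detect a difference in infection or complications between the prosthetics. The sample size is set on recurrence alone, so no power has been reserved for these endpoints. A p-value by itself also does not tell the reader how large a difference is, or what difference has been excluded.

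**Working it through.** **Inputs from the documents.** The test is two-sided. A 0.05 level is stated only for the recurrence calculation and is carried over here. The SAP needs 80 + 40 = 120 patients per arm and enrols 250 (125 per arm). The protocol gives 330 (165 per arm). All three sizes are used because the totals differ.

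**The plan's own figures.** None is given for the endpoints tested by Fisher. The recurrence sample size, "assuming a two-sided 0.05 level test and 80% power", does reproduce with the unpooled formula n = (1.960 + 0.842)² × [p₁(1−p₁) + p₂(1−p₂)] / (p₁−p₂)²:

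- Clean, "hernia recurrence rates of 40% versus 20% for patients receiving biologic versus synthetic prosthetics": 7.849 × (0.24 + 0.16) / 0.04 = 78.5, so 79 (stated 80).
- Contaminated, 60% v 30%: 7.849 × (0.24 + 0.21) / 0.09 = 39.2, so 40 (stated 40).
- Total: 160 + 80 = 240, and 240 / 0.96 = 250, which fits dropout below 5%.

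**Assumptions.** Event rates of 2% to 40% for infection and complications.

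**Step 1: true level and power.** For n per arm, sum Bin(a; n, p₁) × Bin(b; n, p₂) over every pair (a, b) at which the test gives p ≤ 0.05. Setting p₁ = p₂ gives the true level. No simulation is involved.

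True level, Fisher / Pearson chi-square (%):

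| Rate in both arms | 120 per arm | 125 per arm | 165 per arm |
|---|---|---|---|
| 2% | 0.7 / 4.4 | 0.8 / 4.5 | 1.4 / 4.5 |
| 5% | 2.1 / 4.8 | 2.2 / 4.7 | 2.6 / 4.9 |
| 10% | 2.9 / 5.2 | 2.9 / 5.0 | 3.1 / 5.1 |
| 20% | 3.4 / 5.1 | 3.4 / 4.9 | 3.7 / 5.0 |
| 30% | 3.6 / 5.0 | 3.6 / 5.0 | 3.8 / 5.0 |

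Power, Fisher / chi-square (%), with the loss in points:

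| Rates | 120 per arm | 125 per arm | 165 per arm |
|---|---|---|---|
| 5% v 15% | 67.4 / 76.3 (8.8) | 69.8 / 77.4 (7.6) | 83.0 / 87.9 (4.9) |
| 10% v 20% | 51.6 / 59.3 (7.7) | 53.8 / 60.2 (6.3) | 68.0 / 72.9 (5.0) |
| 10% v 25% | 83.7 / 88.0 (4.3) | 85.5 / 88.7 (3.3) | 94.2 / 95.6 (1.4) |
| 15% v 30% | 75.9 / 80.6 (4.7) | 77.7 / 81.7 (4.0) | 88.9 / 91.1 (2.2) |
| 20% v 35% | 70.0 / 74.7 (4.6) | 71.9 / 76.2 (4.4) | 84.2 / 86.9 (2.7) |

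Where Fisher's power is below 85%, the loss is 2.7 to 8.8 points. Above that it shrinks, because there is little room left to lose.

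**Step 2: the stratified test.** Step 1 does not measure the proposed remedy, so CMH was simulated separately (200,000 runs, 125 per arm, stratum sizes equal between arms). For stratum k, with n_k per arm, m_k events in all, a_k of them in one arm, and T_k = 2n_k, reject when |Σ(a_k − m_k/2)| / √Σ[n_k² m_k (T_k − m_k) / (T_k² (T_k − 1))] > 1.96. The two-strata cases put 83 and 42 per arm in the strata, which is close to the SAP's 2:1 split of clean to contaminated.

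Power at an odds ratio of 2.5 (%):

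| Control rates by stratum | Fisher | Chi-square | CMH | CMH, continuity-corrected |
|---|---|---|---|---|
| 10%, 20% | 75.0 | 79.5 | 80.5 | 75.6 |
| 15%, 30% | 85.0 | 87.9 | 88.7 | 85.7 |
| 10%, 40% | 75.4 | 79.7 | 84.1 | 80.0 |
| Eight strata, 5% to 40% | 72.4 | 77.3 | 80.5 | 75.7 |

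With no effect, uncorrected CMH rejects in 4.9% to 5.1% of runs and Fisher in 2.4% to 3.2%.

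**Step 3: where the gain comes from.** Fisher to CMH gains 5.5, 3.8, 8.6 and 8.0 points. Of this, Fisher to chi-square alone gives 4.5, 3.0, 4.3 and 4.8. Stratification adds about 1 point in the first two rows, 4.4 in the third and 3.2 in the fourth. The continuity-corrected CMH gains only about 1 to 5 points over Fisher.

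**The case against.** The strongest defence is that Fisher's test is sound. It holds its level at or below 5% at every event rate, needs no large-sample approximation, and remains valid, if conservative, after stratified randomisation. The protocol lists many separate complications, some of which may be rare. Chi-square can exceed 5%: at most 5.4% at 120 per arm and 5.9% at 40 per arm (the contaminated group), where Fisher's maxima are 3.9% and 3.3%. All of this stands, and it is why an exact test should be kept for rare outcomes.

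Several stronger readings might be inferred, and the documents do not support them:

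- **Fisher costs power and buys nothing.** It buys guaranteed level control.
- **The trial's main safety protection is weakened.** The SAP calls these endpoints secondary. Ongoing oversight runs through review of adverse-event listings and hold rules under the Data and Safety Monitoring Plan, and does not use this test.
- **Contamination is known to be strongly prognostic for infection.** The SAP says that it may double the risk of recurrence. Neither document gives infection rates by stratum, so its effect on infection is an inference.
- **The sample size is undermined.** Recurrence is compared by log-rank, and no stated power rests on Fisher.

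It is also fair to say that Fisher is not the only unstratified test in the SAP. The log-rank comparison of the primary endpoint is unstratified too, and that matters more. The missing effect estimate is likewise a gap in the SAP's specification rather than a property of Fisher's test. Neither point removes the opportunity here.

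**Conclusion.** The point holds as an efficiency improvement to secondary analyses. The planned test does not use the three randomisation factors. Its true level is about 2% to 4% at event rates of 5% to 30%, and lower still for rare events. Against chi-square it gives up about 3 to 9 points of power in the range where power matters, at 120 to 165 per arm. An uncorrected CMH test gains about 4 to 9 points over Fisher at an odds ratio of 2.5 and 125 per arm. Most of that is recovered conservatism unless the strata are strongly prognostic.

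The conservatism follows from the sample size and the test. The size of the power loss rests on assumed event rates. The benefit of stratifying rests on assumed stratum effects, and on stratum sizes balanced between arms. The planned analysis remains valid, and no stated figure fails.

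**What to change.** In the Data Analysis section of the SAP:

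- For binary secondary outcomes with adequate event counts, prespecify a two-sided CMH test **without continuity correction**, stratified by contamination, technique and Charlson score. The correction would forfeit most of the gain when the strata are only moderately prognostic.
- State in advance how Charlson score is collapsed. With two levels there are 2 × 2 × 2 = 8 strata, averaging 240 / 8 = 30 patients.
- Report the stratified risk difference with its 95% CI for each such outcome.
- Keep an exact test for rare complications, with the event-count threshold set before unblinding.
- Consider stratifying the log-rank test in the same edit.

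The cost is SAP wording only: no added data, visits or patients. The statistical price is that guaranteed level control gives way to approximate control near 5%.
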